### 3.5. Stopping Rules

The investigator reserves the right to terminate the study in the interests of patient safety and welfare. The Sponsor reserves the right to terminate the study at any time for administrative reasons.

Patients will also be discontinued from the study if they meet the following criteria:

- ALT or AST  $> 3 \times$  ULN with (or the appearance of) fatigue, nausea, vomiting, right upper quadrant pain or tenderness, fever, rash, and/or eosinophilia  $> 5\%$
- ALT or AST  $> 8 \times$  ULN
- ALT or AST  $> 5 \times$  ULN for more than 2 weeks
- ALT or AST  $> 3 \times$  ULN and bilirubin  $> 2 \times$  ULN or INR  $> 1.5$

For patients meeting the above criteria, the investigator will arrange for the patient to return to the investigational site as soon as possible (within 24 hours of notice of abnormal results) for repeat assessment of ALT, AST, bilirubin, and alkaline phosphatase (ALP), detailed history, and physical examination. Patients will be followed until all abnormalities have normalized (in the investigator's opinion) or returned to the baseline state. If the patient is unable to return to the investigational site, repeat assessments may be performed at a local laboratory.

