### **3.3. Removal of Patients from Therapy or Assessment**

Patients will be allowed to discontinue their participation in the study at any time for any reason (withdrawal of consent). Furthermore, participation in this clinical study may be discontinued by the investigator or by the sponsor for any of the following reasons:

- Intolerable side effects of the study product.
- Changes in medical status or medical condition of the patient such that the investigator believes that patient safety will be compromised or that it would be in the best interest of the patient to stop treatment.
- Patient safety or welfare is at risk.
- Non-compliance with study visits, defined as failure to perform any portion of scheduled assessments or procedures.
- Any unforeseen event that in the opinion of the treating physician and/or the Principal investigator, will prevent the research participant from continuing in this study.
- Sponsor decides to stop the study.

In the event of a patient's withdrawal, the investigator will promptly notify the sponsor. Every effort will be made to complete the end-of-study assessments.

Should any patient choose to withdraw early from the study, they will be advised of the safety precautions to be taken and will be followed until resolution of any AE or until the unresolved AEs are judged by the investigator to have stabilized.

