#### 6.1.5. Clinical Laboratory Assessments

Blood samples for hematology and chemistry assessments and urine sample for urinalysis will be collected during Visit 1 (Day 1), all monthly & quarterly visits, and Visit 7 (End of Study) or Early Withdrawal.

- Hematology: hemoglobin, hematocrit, total and differential leukocyte count, red blood cell (RBC), and platelet count.
- Chemistry: albumin, blood urea nitrogen (BUN), creatinine, total bilirubin, alkaline phosphatase (ALP), aspartate transaminase (AST), alanine transaminase (ALT), sodium ( $Na^+$ ), potassium ( $K^+$ ), chloride ( $Cl^-$ ), lactate dehydrogenase (LDH), uric acid, glucose, and calcium.
- Urinalysis: pH, specific gravity, protein, glucose, ketones, bilirubin, blood, nitrite, leukocyte esterase, and urobilinogen. If protein, occult blood, nitrite, or leukocyte esterase values are out of range a microscopic examination will be performed.

A urine dipstick pregnancy test will be performed on all female post-menarchal patients during at Visit 1 and Visit 7 (End of Study) or Early Withdrawal.

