#### **6.1.8. Adverse Events and Serious Adverse Events**

##### **6.1.8.1. Definition of Adverse Events**

An AE is defined as any untoward medical occurrence in a patient administered a pharmaceutical product during the course of a clinical investigation. An AE can therefore be any unfavorable and unintended sign, symptom, or disease temporally associated with the use of an investigational product, whether or not thought to be related to the investigational product.

Patients will be monitored throughout the study for AEs. Monitoring for treatment-emergent AEs will begin as soon as the patient is dosed. All AEs must be followed until they are resolved or stabilized, or until all attempts to determine resolution of the event are exhausted. The investigator should use their discretion in ordering additional tests as necessary to monitor the progress of such events.

An AE may be:

- A new illness, not documented in the patient's medical history;
- Worsening of a concomitant illness;
- An effect of the study medication; it could be an abnormal laboratory value, as well as a significant shift from baseline within normal range which the qualified investigator or medical qualified designate considers to be clinically important;
- A combination of two or more of these factors.

Surgical procedures themselves are not AEs. They are therapeutic measures for conditions that required surgery. The condition for which the surgery is required is an AE, if it occurs or is detected during the study period. Planned surgical measures permitted by the clinical study protocol and the conditions(s) leading to these measures are not AEs, if the condition(s) was

(were) known before the start of study treatment. In the latter case, the condition should be reported as medical history.

Absence seizures will not be considered AEs. However, new seizure types and injury resulting from a seizure will be captured as AEs.

Patients will be monitored throughout the study for AEs. All AEs must be followed until they are resolved or stabilized, or until all attempts to determine resolution of the event are exhausted. The investigator should use his/her discretion in ordering additional tests as necessary to monitor the progress of such events.

Adverse events reported prior to dose administration will be recorded as part of the patient's medical history.

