**6.1.8.8. Adverse Event Follow-Up**

All non-serious AEs that are not related or unlikely to be related to study treatment will be followed until the end of study participation. All SAEs or AEs that are considered as possibly, probably, or definitely related to treatment will be followed until resolution or stabilization.

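### Two liver stopping criteria in Section 3.5 (ALT/AST above 5x ULN for over 2 weeks; INR above 1.5) have no planned measurement that lets them be judged on time

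*Combined protocol and SAP*

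**What the plan says.** Section 3.5 (Stopping Rules) gives four liver grounds for discontinuing a patient. In summary:

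1. ALT or AST above 3x ULN with listed symptoms or eosinophilia above 5%.
2. ALT or AST above 8x ULN.
3. ALT or AST above 5x "ULN for more than 2 weeks".
4. ALT or AST above 3x ULN with bilirubin above 2x ULN or INR above 1.5.

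The recall follows: "For patients meeting the above criteria, the investigator will arrange for the patient to return to the investigational site as soon as possible". The time limit is 24 hours after the site learns of the result. The content of the recall visit is "repeat assessment of ALT, AST, bilirubin, and alkaline phosphatase (ALP), detailed history, and physical examination". A local laboratory may be used if the patient cannot return to the site.

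Section 6.1.5 sets the scheduled blood tests. The chemistry list begins "Chemistry: albumin, blood urea nitrogen (BUN), creatinine, total bilirubin, alkaline phosphatase (ALP), aspartate transaminase (AST), alanine transaminase (ALT" and continues with electrolytes, LDH, uric acid, glucose and calcium. Hematology is blood counts with a differential. Table 1 places these draws at Day 1, Weeks 4, 8, 12, 24 and 36 (each ±5 days), and Week 48 (±3 days) or Early Withdrawal.

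The general adverse-event text also applies. Section 6.1.8.1 says "All AEs must be followed until they are resolved or stabilized, or until all attempts to determine resolution of the event are exhausted" and adds "The investigator should use their discretion in ordering additional tests as necessary to monitor the progress of such events". Section 6.1.8.8 says "All SAEs or AEs that are considered as possibly, probably, or definitely related to treatment will be followed until resolution or stabilization". Section 3.3 permits withdrawal for "Changes in medical status or medical condition of the patient such that the investigator believes that patient safety will be compromised".

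**The concern.** Criterion 3 is about persistence, so it needs a second value just after two weeks. The INR part of criterion 4 needs an INR. The protocol makes both grounds for mandatory discontinuation but plans neither measurement at the time it is needed. The one timed repeat starts only after some criterion has been met, which is too late to help decide whether criterion 3 or the INR part of criterion 4 is met.

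At stake is continued dosing, at up to 40 mg/kg/day, in a child whose transaminases may already justify stopping. The protocol itself treats the signal as important. Section 6.1.8.1 makes transaminase elevation an event of special interest. Section 3.2.2 (exclusion 6) lists ALT/AST at or above 3x ULN among the abnormalities that bar entry. Section 4.7.2 allows valproate, for which Section 1.4 lists liver failure as a side effect. The protocol also writes reflex tests elsewhere: direct bilirubin after an abnormal total bilirubin (Table 1, footnote c), and urine microscopy after certain abnormal dipstick results (Section 6.1.5). It has none for ALT or AST.

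**Working it through.** The plan states no figure to reproduce here. The check sets a first result against each criterion, then measures the gaps between scheduled draws.

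**Step 1. A first isolated value against Section 3.5.** Take ALT or AST above 5x and up to 8x ULN, with no listed symptoms, eosinophilia at most 5% and bilirubin at most 2x ULN.

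- Criterion 1: not met (no symptom, no eosinophilia).
- Criterion 2: not met (8x is not above 8x).
- Criterion 3: cannot be met on one value.
- Criterion 4: bilirubin part not met; INR part unknown, because INR is not measured.

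No criterion is shown to be met, so the 24-hour recall does not apply.

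**Step 2. Time to the next scheduled draw.** Inputs are the Table 1 time points and windows. The gap is the nominal difference, plus or minus the sum of the two windows. The delay is the gap minus 15, because day 15 is the first day beyond two weeks.

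| Interval | Nominal gap (days) | Range with windows | Nominal delay after day 15 | Range of delay |
|---|---|---|---|---|
| Day 1 to Week 4, 4 to 8, 8 to 12 | 28 | 28 ± (5+5) = 18 to 38 | 28 − 15 = 13 | 3 to 23 |
| Week 12 to 24, 24 to 36 | 84 | 84 ± (5+5) = 74 to 94 | 84 − 15 = 69 | 59 to 79 |
| Week 36 to 48 | 84 | 84 ± (5+3) = 76 to 92 | 84 − 15 = 69 | 61 to 77 |

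Two conventions affect the ranges. If windows are counted from the actual Day 1, the first interval is 28 ± 5 = 23 to 33 days, a delay of 8 to 18. If Visit 7 takes the ±2 weeks that Section 3.1 gives for the Safety Period, the last interval is 84 ± (5+14) = 65 to 103 days. In every case the gap exceeds 14 days. The 84-day gaps cover (48 − 12)/48 = 75% of the treatment period.

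**Step 3. INR.** INR is absent from the Section 6.1.5 panels, from Table 1 and from the Section 3.5 repeat list. Only the Section 6.1.5 and Table 1 omissions matter for deciding criterion 4, since patients who reach the repeat list already meet a criterion. Total bilirubin is drawn at every scheduled visit, so the bilirubin part of criterion 4 works.

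**Step 4. Does other text supply the missing test?** Sections 6.1.8.1 and 6.1.8.8 impose a duty to follow events but set no trigger, interval or analytes. Extra tests are discretionary. Section 3.3 permits withdrawal but orders no test. Section 3.1.1 refers overall safety review to Section 10.3, which is a sponsor data review before database lock. The Data Monitoring Committee is mentioned only for approving dose levels in INS011-17-103.

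**The case against.** The strongest reply is that follow-up is mandatory, not optional. Adverse events must be followed, a laboratory value the investigator considers clinically important can be one, and transaminase elevation is a named event of special interest. A site holding a value above 5x ULN would see that it needs a second value to apply criterion 3. Discretionary dose changes (Section 3.4) and withdrawal (Section 3.3) are also available, and criterion 1 can be met between draws if symptoms appear. All of this stands, and a careful investigator would retest early. But none of it fixes when or what to test, so waiting for the next scheduled draw would still be within the protocol.

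Three further limits stand.

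- **Values above 3x and up to 5x ULN.** A reader might extend the delay to these. The documents do not support that: no criterion for such values depends on elapsed time. Only the missing INR affects them.
- **Visit 1.** A reader might infer that children enter with raised values unnoticed. Exclusion 6 bars clinically significant abnormalities in the previous 14 days, including ALT/AST at or above 3x ULN. A Visit 1 case therefore needs a new rise since that screen. It remains possible, because Section 7.1.1 has blood drawn and drug dispensed at the same visit.
- **Frequency.** At most 30 patients will enroll. Section 1.3 reports a completed long-term study of 52 children with seven early terminations, none attributed to transaminase elevation. This suggests the event that matters here may be uncommon, but it gives no rate for isolated elevations.

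**Conclusion.** The point holds. On planned data, criterion 3 cannot be judged on time and the INR part of criterion 4 cannot be judged at all. For a first isolated value above 5x and up to 8x ULN, the persistence decision comes nominally 13 days after day 15 in the monthly phase and 69 days after it in the quarterly phase. These figures assume no unscheduled retest and use day 15 as the comparator; the protocol names no retest day. No patient count can be estimated.

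A reader might conclude that the liver stopping rules as a whole do not work. They do not fail in that way: the criteria for values above 8x ULN, and for values above 3x ULN with raised bilirubin or eosinophilia, can be decided from the first scheduled result. Nor does the protocol direct anyone to wait 12 weeks; it allows it. The gap should be closed because a mandatory safety rule ought not to depend on discretion for the data that trigger it.

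**What to change.** Add one rule to Section 3.5. For any on-study ALT or AST above 3x ULN that meets no stopping criterion, repeat ALT, AST, total bilirubin and ALP promptly, with INR added. Within 72 hours would be reasonable; that interval is a suggestion, not taken from the documents. If the value was above 5x ULN, repeat again at about day 15 so that criterion 3 can be decided. Extend the existing local-laboratory allowance to these repeats.

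Adding INR to the current repeat list is optional. It would inform care of patients already being discontinued, but would not serve criterion 4.

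The cost is one or two unscheduled blood draws in affected children only. The visit schedule, dispensing and analyses do not change.

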## 4. TREATMENTS

### 4.1. Treatments Administered

Patients or parent/caregiver will be reminded how to measure, take their dose, and record their dose in the dosing diary when the IP is dispensed for the first time.

Total daily doses ranging from 20 mg/kg/day to 40 mg/kg/day will be administered with food, within 30 minutes after a meal, in two equivalent daily doses approximately every 12 hours.

### 4.2. Identity of Investigational Product

The active pharmaceutical ingredient (API) in Cannabidiol Oral Solution is a pharmaceutical grade synthetic CBD manufactured according to cGMP. It is an off-white to pale yellow resin or crystal substance that is soluble in several organic solvents with an acid dissociation constant (pKa) of 9.64. The solution is a clear, colorless to pale yellow-brown colored solution (CBD concentration of 100 mg/mL) filled into a 30 mL amber glass vial. More detailed information may be found in the IB.

### 4.3. Method of Assigning Patients to Treatment Groups

Patients will be allocated to a dose of the investigational product based on their dosing in the previous study INS011-17-103.

### 4.4. Selection and Timing of Dose for Each Patient

Once the informed consent for INS011-17-113 is provided, patients will initiate this long-term safety study on the final dose of CBD administered during the study INS011-17-103 Visit 6 (End of Study). Subsequently, the dose may be increased to a maximum of 40 mg/kg/day only if the higher dose level has been approved by the Data Monitoring Committee in INS011-17-103.

Patients will take each dose approximately every 12 hours with food in order to ensure consistent plasma levels are achieved. The date and time of all investigational product administrations will be documented in the case report form (CRF).

### 4.5. Blinding and Unblinding Treatment Assignment

Not applicable. This is an open-label study.

### 4.6. Treatment Compliance

The prescribed dosage, timing, and mode of administration of IP may not be changed except as directed by the investigator.

The investigator, a member of the investigational staff, or a hospital pharmacist must maintain an adequate record of the receipt and distribution of all study medication using the Drug Accountability Form. These forms must be available for inspection at any time.

All supplies of IP should be accounted for at the termination of the study and a written explanation provided for discrepancies. All used and unused supplies, and packaging materials are to be inventoried and returned to the Sponsor or a designee by the investigator. The

investigator is not permitted to return or destroy unused clinical drug supplies or packaging materials unless authorized by the Sponsor or a designee.

If the study is terminated, discontinued, suspended, or completed, all used and unused supplies of the investigational product may be destroyed via the use of a third-party vendor or be returned to the Sponsor or a designee after the final drug accountability check has been performed. A certificate of destruction will be provided to the Sponsor.

All regulations issued by the DEA concerning the accountability of Schedule I medications will be followed (e.g., prevention of diversion).

## **4.7. Permitted and Prohibited Therapies**

### **4.7.1. Permitted Therapies**

Any medications (other than those excluded by the protocol, see Section 4.7.2) that the investigator considers necessary for a patient's welfare and will not interfere with the investigational product may be administered at the investigator's discretion.

### **4.7.2. Prohibited Therapies**

During the Safety, Taper, and Follow-up Periods, patients are not to receive the following:

- Any cannabinoids besides the study drug (cannabidiol,  $\Delta^9$ -THC, hemp oil, Realm Oil or marijuana).
- Phenytoin, fluvoxamine, carbamazepine, or St. John's Wort.
- Medications that are strong inhibitors/inducers/sensitive substrates with a narrow therapeutic index for CYP3A4, CYP2C9, or CYP2C19, with the exception of Valproic Acid.
- Any other investigational drug or investigational device.

Although they are not prohibited, patients taking concomitant medications may need to be monitored with special care to identify any AEs arising due to the potential for altered drug metabolism.

## **4.8. Treatment After the End of Study**

After the Safety Period, patients will have their taper schedule initiated over a 0-10 days period.

## 5. STUDY DRUG MATERIALS AND MANAGEMENT

### 5.1. Labeling and Packaging

#### 5.1.1. Labeling

The labels for the investigational product will contain all information according to regulatory requirements.

#### 5.1.2. Packaging

The investigational product will be supplied in 30 mL containers of a 100 mg/mL strength (i.e., 3000 mg per container).

Non-proprietary or common name of drug product	Cannabidiol Oral Solution, 100 mg/mL
Dosage form	Oral solution
Strength	100 mg/mL

Please refer to the Cannabidiol Oral Solution IB for additional information on the drug formulation.

The investigational product will be clearly marked according to FDA and/or ICH requirements regarding use for clinical study investigation only and will be labeled with the investigational product name, study reference number, storage conditions, and expiry date. It is the responsibility of the investigator to ensure that accurate accountability records are maintained throughout the study. Study center staff will dispense the investigational product according to the handling instructions.

### 5.2. Dispensing and Storage

IP will be stored at controlled room temperature (20 to 25 degrees Celsius, 68 to 77 degrees Fahrenheit) at the study centers.

Cannabis and its constituents (including CBD) are **Schedule I** controlled substances and subject to all applicable local and federal laws and regulations regarding these products. This includes security provisions for storing the controlled substances and for dispensing in a manner to prevent diversion. Additionally, the Sponsor or investigator must provide a statement of the quantity to be manufactured and the sources of the chemicals to be used or the substance.

The DEA regulations detail specific security requirements for storage of the investigational product. Licensed practitioners must store controlled substances in a “securely locked, substantially constructed cabinet” and must notify the DEA of the theft or significant loss of any controlled substances within one business day of discovering such loss or theft. Furthermore, all practitioners are prohibited from hiring employees who have been convicted of a drug-related felony or who have had a DEA registration denied or revoked.

Investigators are responsible for ensuring that all applicable licensures are in place and storage conditions are appropriate.

Doses of IP will be administered from the Schedule I-licensed study center.

The study centers are required to provide complete information, including case report forms (CRFs) and final outcomes, on all instances of addiction, abuse, misuse, overdose, drug diversion/drug accountability, discrepancies in amount of the clinical supplies of the investigational product, noncompliance, protocol violations, lack of efficacy, individuals lost to follow-up, and any other reasons why patients dropped out of the study.

### **5.3. Drug Supply and Accountability**

The investigator, a member of the investigational staff, or a hospital pharmacist must maintain an adequate record of the receipt and distribution of all study medication using the Drug Accountability Form. These forms must be available for inspection at any time.

All supplies of Cannabidiol Oral Solution should be accounted for at the termination of the study and a written explanation provided for discrepancies. All unused supplies and packaging materials are to be inventoried and returned to the Sponsor or a designee by the investigator. The investigator is not permitted to return or destroy unused clinical drug supplies or packaging materials unless authorized by the Sponsor or a designee.

If the study is terminated, discontinued, suspended, or completed, all unused supplies of the investigational product may be destroyed via the use of a third-party vendor or be returned to the Sponsor or a designee after the final drug accountability check has been performed. A certificate of destruction will be provided to the Sponsor.

All regulations issued by the DEA concerning the accountability of Schedule I medications will be followed (e.g., prevention of diversion).

